10.9.2 Urgent Safety Measures

An urgent safety measure (USM) is a procedure not defined by the protocol, which is put in place prior to authorisation by the MHRA and REC in order to protect clinical trial participants from any immediate hazard to their health and safety.

The sponsor or delegate will notify the MHRA and REC immediately and, in any event, within 3 days that such a measure has been taken and the reasons why it has been taken. The initial notification to the MHRA will be by telephone (ideally within 24 hours) and a notice in writing will be sent within 3 days, setting out the reasons for the USM and the plan for further action. After discussion with the MHRA and REC, further action will be agreed, which may include submission of a substantial amendment, a temporary halt, or permanent termination of the trial.

If the study is temporarily halted it may not recommence until authorised to do so by the MHRA and REC. If the study is permanently terminated before the date specified for its conclusion (in the original applications to MHRA and REC), the sponsor should notify the MHRA and MREC within 15 days of the date of termination by submitting the formal End of Trial Notification.

10.10 Contact Details and Out-of-hours Medical Cover

Parents will be directed to contact the research team at their CF centre or shared care centres should medical advice be required during office hours. 24 hour access to specialist medical advice is not considered necessary due to the studies low risk level. If medical advice is required outside of office hours then the parent of the participant will be advised to seek usual medical advice.

11 STATISTICAL CONSIDERATIONS

11.1 Method of Randomisation

Participants will be randomised using a secure (24-hour) web based randomisation programme monitored by the Registry team with CTRC oversight to ensure allocation concealment. Randomisation lists will be generated in a 1:1 ratio using simple block randomisation with random variable block length. Factors within this protocol that are being used to stratify randomisation will not be disclosed to prevent prediction in this open trial.

11.2 Sample Size calculation

The sample size is based on “time to first identification of PsA on respiratory culture (any type) following randomisation and treatment allocation”. Data on this outcome have become available from the UK and US Registries. Combined data on 9250 infants with CF demonstrate a median age of acquisition of approximately 40 months (unpublished data from [name]’s group, available on request). A reduction in the age of acquisition by 12 months (to 28 months) was considered clinically significant by stakeholders (Physicians survey) and PPI representatives and both confirmed that any longer than 12 months would be a concern to them. The trial was therefore powered to provide confidence that “*Prevent and Treat*” would not be considered inferior as long as the median age to acquisition of PsA was no more than 12 months shorter than “*Detect and Treat*”.

Assuming approximately 10% attrition, we will recruit 480 infants, with the aim of comparing 220 in each arm, per protocol analysis. With 220 in each arm, a test of non-inferiority of the intervention group (“*Prevent and Treat*”) compared to the standard group (“*Detect and Treat*”) with a 2.5% one-sided significance level will have 80% power to reject the null hypothesis of non-inferiority (a hazard ratio of 1.54 or greater) when the “*Detect and Treat*” exponential parameter (λ s) is 0.0173 and the true hazard ratio is 1.0.

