3.2.3 The rationale for the trial design (non-inferiority)

For the results of CF START to translate to a change in practice, we need to be able to deliver confidence that ASAP does not result in a significant increase in earlier *PsA* growth and this has been the rationale underpinning our trial design and power calculations. Although the non-inferiority design was considered optimal to provide confidence in our result, this was a challenging concept to explain to PPI groups, who felt any increase in the potential to grow *PsA* from respiratory cultures would be a concern. A survey of all Paediatric CF Physicians in the UK supported a power calculation based on UK CF Registry data that would provide confidence that if a difference exists between the two treatment arms, this would be no more than 12 months earlier.

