11.3 Interim Monitoring and Analyses

No formal interim analyses of primary or secondary outcomes will be performed but analyses of the accumulating data (recruitment, protocol deviations, baseline characteristics, compliance, withdrawals, missing data and safety data) will be performed at regular intervals (at least annually) for review by an IDSMC. These analyses will be performed by the CTU trial statistician. The IDSMC will be asked to give advice on whether the accumulated data from the trial, together with results from other relevant trials, justifies continuing recruitment of further participants or further follow-up. A decision to discontinue recruitment, in all participants or in selected subgroups will be made only if the result is likely to convince a broad range of clinicians including participants in the trial and the general clinical community. If a decision is made to continue, the IDSMC will advise on the frequency of future reviews of the data on the basis of accrual and event rates. All closed results (results split by treatment) will be confidential to the IDSMC members and will not be for review by the trial management group (except the statistical team preparing the IDSMC report). The IDSMC members will make formal recommendations to the trial working group and TSC (see section 15.4.2) regarding the continuation of recruitment of participants into the trial and will comply with a trial-specific IDSMC charter according to ICH GCP guidelines. The IDSMC will be asked to consider participant safety, particularly any Sudden Unexpected Serious Adverse Reactions (SUSARs) leading to death, alongside treatment efficacy when making their recommendation regarding continuation, amendment or discontinuation of the trial.

A report shell will be discussed with the IDSMC at its first meeting before recruitment starts and circulated prior to the first report being produced. Analysis Plan

The primary end-point will be analysed on an intention to treat basis and the analysis of time to first growth of PsA will be summarised by Kaplan-Meier curves for each treatment group and compared overall using the logrank test and survival regression methods. Non-inferiority of the “*Prevent and Treat*” group will be accepted in a 0.025 level test, if the upper boundary of the 97.5% confidence interval around the hazard ratio lies below 1.54.

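### The non-inferiority margin of 1.54 is looser than the agreed 12-month limit (hazard ratio 1.43 under the protocol's own model), and the stated 80% power belongs to 1.43

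*Protocol*

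**What the plan says.** Section 11.2 starts from registry data that "demonstrate a median age of acquisition of approximately 40 months". It then sets the clinical limit: "A reduction in the age of acquisition by 12 months (to 28 months) was considered clinically significant by stakeholders", and the trial is powered so that *Prevent and Treat* is not inferior if its median is at most 12 months shorter. Section 3.2.3 reports the same limit from the survey of physicians: any difference "this would be no more than 12 months earlier".

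The calculation in 11.2 is made "with a 2.5% one-sided significance level". It says that the test with 220 per arm "will have 80% power to reject the null hypothesis of non-inferiority (a hazard ratio of 1.54 or greater"), when the control exponential parameter "is 0.0173 and the true hazard ratio is 1.0". The analysis plan text within 11.3 accepts non-inferiority "if the upper boundary of the 97.5% confidence interval around the hazard ratio lies below 1.54".

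**The concern.** The protocol gives the tolerated difference twice, once in months and once as a hazard ratio, and names the exponential model that links them. Under that model the two do not match: 1.54 is the wider limit. The hazard ratio is what decides the trial, so prophylaxis could be called not inferior under a limit wider than the one physicians and family representatives accepted. Section 11.2 says both groups would be concerned by anything longer than 12 months. The stated power would also not be the power of the stated design.

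**Working it through.** **Inputs.** One-sided α 0.025, power 80%, true hazard ratio 1.0, λ = 0.0173 per month, 220 per arm, margin 1.54 (Section 11.2). Allocation 1:1 (11.1). Entry at 70 days or less (6.1) and follow-up to age 48 months (8.1), so T is about 46 to 48 months. Section 11.2 does not state T; it is taken from 6.1 and 8.1.

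**Step 1: model.** ln 2 / 40 = 0.01733, so λ = 0.0173 is an exponential with a median of 40 months.

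**Step 2: margin against months.** Under exponential times the hazard ratio is the inverse ratio of the medians.
- 12 months earlier: 40/28 = 1.429.
- Margin 1.54: 40/1.54 = 26.0 months, which is 14.0 months earlier.

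**Step 3: sample size and power.** Events needed = 4(1.960 + 0.8416)² / (ln m)². Event probability P = 1 − exp(−0.0173 T), which is 0.549 at T = 46 and 0.564 at T = 48. Number per arm = events / (2P). Power = Φ(ln m × √d / 2 − 1.960), where d = 440P is 241.5 or 248.2 events.

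| | m = 1.54 (as stated) | m = 40/28 |
|---|---|---|
| Events for 80% power | 168.4 | 246.8 |
| Per arm, T = 48 / 46 | about 149 / 153 | about 219 / 225 |
| Power with 220 per arm, T = 48 / 46 | 92.5% / 91.8% | 80.2% / 79.1% |

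For example, at T = 48 the power for 1.54 is Φ(0.4318 × 15.755/2 − 1.960) = Φ(1.44) = 0.925.

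The stated pair of 220 per arm and 80% power is therefore not reproduced with 1.54, but is reproduced with 1.43. Solving instead for the margin that gives 80% power with 440 infants, exp(2 × 2.8016/√d), returns 1.427 (T = 48) to 1.434 (T = 46). Freedman's formula at T = 48 gives 91.8% and 79.4% for the two margins. A simulation of 4,000 trials with a Cox analysis gives 91.9% and 80.0%. Exponential dropout of 10% gives 91.4% at 1.54.

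**Step 4: consequence for the decision.** Suppose the true hazard ratio is exactly the 12-month limit. Then P(non-inferiority declared at 1.54) = Φ((ln 1.54 − ln 1.429) × √d / 2 − 1.960). With the events expected under that alternative (270 at T = 46, 277 at T = 48) this is 9.0% to 9.1%; simulation gives 9.4%. With margin 1.43 it is 2.5% by construction.

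The largest observed hazard ratio that passes, exp(ln m − 1.960 × 2/√d), is about 1.20 with margin 1.54 and 1.11 with 1.43. In medians these are 40/1.20 = 33.3 and 40/1.11 = 36.0 months.

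**The case against.** - **1.54 is used consistently.** It stands in both 11.2 and 11.3, and the chronology in 17.2 lists its introduction as a typographical correction, so it may be deliberate. That stands as a reason to ask the sponsor how it arose. But no section derives it, and the conflict lies within the current 11.2.
- **Other inputs could give 220 per arm at 1.54.** About 28 months of follow-up would do it, as would a one-sided 0.0125 level with 36 months. The protocol states 2.5% one-sided and follow-up to age 48 months, so neither is available. The match to 1.43 does depend on reading T from 8.1.
- **Time could run from randomisation.** Section 11.2 uses time after randomisation but quotes a median age. With entry at 70 days (2.3 months), the 12-month limit becomes 37.7/25.7 = 1.467, and 1.54 allows about 13.2 months. The excess is then about 1 month instead of 2, and the false-claim probability about 6% instead of 9%. This softens the point but does not remove it. Reaching 1.54 would need an origin near 5.8 months of age, which the entry limit excludes.
- **Event times may not be exponential.** A Weibull shape of ln 1.54 / ln 1.429 = 1.21 would make 1.54 equal to 12 months. The text specifies an exponential parameter, and this reading would leave the stated power unexplained.
- **The practical harm is limited.** A positive result still needs an observed hazard ratio of about 1.20 or less, a median roughly 7 months earlier. The 9% applies at a true difference of exactly 12 months and falls to 2.5% at 14. If the 97.5% interval in 11.3 were two-sided, it would be about 5%. These are fair limits on the size of the problem. The two-sided reading is the less likely, because 11.3 also specifies a 0.025-level test.

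**Conclusion.** The concern holds. Under the protocol's exponential model with a 40-month control median, the 12-month limit is a hazard ratio of 1.43, whereas 1.54 allows 14.0 months (about 13.2 if time runs from randomisation at 70 days). With follow-up to age 48 months, the stated 220 per arm and 80% power fit 1.43; at 1.54 the power is about 92%, and about 150 per arm would suffice. At a true 12-month disadvantage, the chance of a false non-inferiority claim is about 9% (about 6% from randomisation) against the intended 2.5%. This affects the primary decision rule and must be resolved before analysis.

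**What to change.** Replace 1.54 by 1.43 (40/28) in Section 11.2 and in the decision rule in 11.3. State the follow-up assumed and whether the 12 months is measured from birth or from randomisation. Keep 480 recruited, and give power as about 79–80% with 440 evaluable, or 78–80% with 432 (480 less 10%).

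If the sponsor does intend 1.54, the protocol should instead state the tolerated difference as 14 months, record the stakeholders' agreement to it, and restate power as about 92%.

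The same edit should settle two wordings in these paragraphs. The null hypothesis should be named as inferiority (hazard ratio at or above the margin). The rule should refer to the upper limit of the two-sided 95% interval, equivalently a one-sided 97.5% limit; read as a two-sided 97.5% interval, power at 1.43 would be only 70–72%. Separately, the hypothesis in 3.4 is worded opposite to the primary objective and should be aligned.

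**Cost.** No extra participants, but a protocol amendment, which Section 15.2 says the funder must approve before it is submitted. The stricter margin also raises the chance of missing non-inferiority when the arms are truly equal, from about 8% to about 20–22%. The 20% is the risk that the stated 80% power already accepts.

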11.3 Interim Monitoring and Analyses

No formal interim analyses of primary or secondary outcomes will be performed but analyses of the accumulating data (recruitment, protocol deviations, baseline characteristics, compliance, withdrawals, missing data and safety data) will be performed at regular intervals (at least annually) for review by an IDSMC. These analyses will be performed by the CTU trial statistician. The IDSMC will be asked to give advice on whether the accumulated data from the trial, together with results from other relevant trials, justifies continuing recruitment of further participants or further follow-up. A decision to discontinue recruitment, in all participants or in selected subgroups will be made only if the result is likely to convince a broad range of clinicians including participants in the trial and the general clinical community. If a decision is made to continue, the IDSMC will advise on the frequency of future reviews of the data on the basis of accrual and event rates. All closed results (results split by treatment) will be confidential to the IDSMC members and will not be for review by the trial management group (except the statistical team preparing the IDSMC report). The IDSMC members will make formal recommendations to the trial working group and TSC (see section 15.4.2) regarding the continuation of recruitment of participants into the trial and will comply with a trial-specific IDSMC charter according to ICH GCP guidelines. The IDSMC will be asked to consider participant safety, particularly any Sudden Unexpected Serious Adverse Reactions (SUSARs) leading to death, alongside treatment efficacy when making their recommendation regarding continuation, amendment or discontinuation of the trial.

A report shell will be discussed with the IDSMC at its first meeting before recruitment starts and circulated prior to the first report being produced. Analysis Plan

The primary end-point will be analysed on an intention to treat basis and the analysis of time to first growth of PsA will be summarised by Kaplan-Meier curves for each treatment group and compared overall using the logrank test and survival regression methods. Non-inferiority of the “*Prevent and Treat*” group will be accepted in a 0.025 level test, if the upper boundary of the 97.5% confidence interval around the hazard ratio lies below 1.54.

Given that ITT analysis is likely to be anticonservative when testing for non-inferiority, secondary analysis will be undertaken to estimate efficacy of treatment, factoring out deviation from randomised treatment. In order to prevent selection bias associated with standard per protocol analysis (whereby participants are censored at the time of treatment deviation), a complier average causal effect (CACE) will be estimated using a rank-preserving structural failure time model (RPSFTM) as described by Robins (11). The RPSFTM retains the balance afforded by randomisation while adjusting for direct switches between trial treatments, providing an estimate of treatment effect in the absence of such switches. However given the difficulties associated with data capture of daily fluctuations in dose, this RPSFTM estimate will not adjust for everyday variation in treatment receipt, thus providing an estimate that is generalisable to usual conditions of use.

Characteristics of continuous data will be expressed as the mean (+/-SD) and median (interquartile range). Differences will be examined using the Student’s t test or the Mann-Whitney rank sum test, depending on the distribution of the data and will include the appropriate confidence interval.

For binary data, proportions will be reported for both treatment groups and the relative risk and corresponding 95% confidence interval will also be reported.

Missing data will be monitored and strategies developed to minimise its occurrence. Missing data will be handled by considering the robustness of the complete case analysis to sensitivity analyses using various imputation assumptions; however these will be informed by data collected on the reasons for missing data.

A full statistical analysis plan will be written prior to any data being analysed that will describe in detail the methodology that is described above.

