3.4 Objectives

We hypothesise that the use of ASAP (flucloxacillin) predisposes infants with CF to earlier airway infection with *PsA* compared to infants treated with antibiotics in more targeted manner. CF START is a Randomised open label registry trial to assess the safety and efficacy of flucloxacillin as a long term prophylaxis agent for infants with CF.

4 Trial design

CF START is an open label randomised controlled trial employing a parallel group design to compare two treatment strategies. The non-inferiority design is aimed to provide confidence to stakeholders that the currently employed treatment strategy (“*Prevent and Treat*”) does not predispose infants with CF to significantly earlier airway infection with *PsA* compared to infants treated with antibiotics in a more targeted manner (“*Detect and Treat*”).

In addition, CF START will provide valuable data on the effectiveness of this intervention. To achieve this we will collect data over a relatively long time period (up to 48 months of age) and to facilitate this trial design, we are employing an innovative approach, namely the collection of outcome from a national Registry.

Table 1: Summary of Objective, Outcomes and Timepoints

Primary Objective	Outcome Measures	Timepoint(s) of evaluation of this outcome measure
To demonstrate that infants on ASAP (“ Prevent and Treat ”) are not predisposed to earlier airway infection with PsA	Age at first growth of PsA from respiratory culture collected as part of routine care	All encounters to trial completion (age, 48 months)
Secondary Objective	Outcome Measures	Timepoint(s) of evaluation of this outcome measure
To determine if ASAP improves respiratory function in pre-school children with CF	Lung clearance index measured by the multiple breath washout technique	One trial visit between age 40-48 months
To determine the need for extra antibiotic treatment	Number of courses and total number of days of extra antibiotics (oral, intravenous and aerosolised)	All encounters to trial completion (age, 48 months)
To determine the number and type of respiratory culture taken during the trial period	Number and type of respiratory culture	All encounters to trial completion (age, 48 months)
To determine the number and proportion of respiratory cultures positive for SA	Positive respiratory cultures for SA	All encounters to trial completion (age 48 months)

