To determine the number and proportion of respiratory cultures positive for PsA	Positive respiratory cultures for PsA	All encounters to trial completion (age, 48 months)
To determine the number and proportion of respiratory cultures positive for other significant CF pathogens	Positive respiratory cultures for other significant CF pathogens	All encounters to trial completion (age, 48 months)
To determine if there is evidence of chronic airway infection	More than 50% of respiratory cultures are positive for the same pathogen during any 12 month period during the trial	All encounters to trial completion (age, 48 months)
To determine the frequency of hospital admission	Number of inpatient stays and number of days	All encounters to trial completion (age, 48 months)

To identify any adverse events	-Annual blood test results (including liver function tests) -Annual ultrasound scan of liver, if available -Reports of complications (ABPA, CFRD, CFRLD)	All encounters to trial completion (age, 48 months)
To determine nutritional status	Weight, height and weight for height percentile	At 48 months (or as near to study end as possible)
To identify method of participant feeding	Feeding by: 
 • Breast • Bottle • Combination of breast and bottle Participants breast fed for >3 months will be considered exclusively breast fed in the final analysis.	At 6 months (or as near to 6 months as possible)
To determine the costs to the NHS	CF banding* and treatment costs	All encounters to trial completion (age, 48 months)

* Banding data will be collected separately

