8.2.2 Review of concomitant medication

In order to determine the need for extra antibiotic all medication taken during the course of the study will be recorded on the UK CF Registry at each encounter, if applicable, as per standard care. Extra antibiotics are defined as any additional antibiotics (type and dose) to those prescribed on the randomised trial arm. Data recorded will include total number of courses of extra antibiotics and total number of days. The antibiotics will be divided into oral, aerosolised (nebulised) and intravenous.

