8.2.4 Weight and Height measurement

Weight and height are measured and recorded at each clinic visit. Entry of these data on the Registry is mandatory to complete an encounter. Weight and height data will be collected throughout the trial but the analysis will focus on this outcome in the last 8 months of the trial (age 40-48 months). Weight and height will be recorded as SD for age. In addition the weight for height percentile will be calculated

Weight for height percentile will be calculated using age appropriate formulae.

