9.5.3 Data on Concomitant Medication

The dose and name of all chronic concomitant medications will be documented on the UK CF Registry. The PI or delegated research member should reassess concomitant medications at each clinic visit. Any medications introduced/discontinued or any changes to current medications should be documented on the UK CF Registry.

At each encounter the CF team will record (name, dose and duration) any additional antibiotics (oral/ IV) prescribed since the last encounter.

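### The t test or Mann-Whitney rule for secondary outcomes ignores follow-up time for antibiotic and admission totals, leaves baseline size out of the growth comparison, and lets prophylaxis after a switch count as extra antibiotic

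*Protocol*

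**What the plan says.** The analysis text in Protocol 11.3 gives two rules for outcomes other than the primary. Binary data get proportions and a relative risk. Continuous data get Student's t test "or the Mann-Whitney rank sum test, depending on the distribution of the data", and the comparison "will include the appropriate confidence interval". No covariate, person-time term or separate method for counts is stated. The statistical analysis plan is to set out in detail the methods already described there.

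Table 1 in Section 4 defines the outcomes concerned as totals over the trial: "Number of courses and total number of days of extra antibiotics (oral, intravenous and aerosolised") and "Number of inpatient stays and number of days". Section 8.5.3 keeps a withdrawn child's data up to withdrawal and collects nothing afterwards.

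Section 8.2.2 defines the antibiotic outcome: "Extra antibiotics are defined as any additional antibiotics (type and dose) to those prescribed on the randomised trial arm". Section 8.5.2 names a change from Detect and Treat to Prevent and Treat as an example of leaving the allocated arm. Section 9.2.4 allows an alternative prophylactic antibiotic after persistent intolerance.

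For growth, 8.2.4 uses SD scores for age. Section 7.4 lists height, weight, birth weight and gestation as baseline data, but no stated analysis uses them.

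**The concern.** A raw total treats a child observed for one year like a child observed for four. If one arm loses more children, its totals fall for that reason alone, and neither test can tell this from a treatment effect. The two tests also address different quantities, a mean difference and a shift in ranks, so choosing between them on the observed data leaves the reported effect undefined until the data are seen.

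The antibiotic outcome is meant to show the need for additional treatment. If long-term prophylaxis enters the same total, the figure mixes two things that the trial sets out to contrast.

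For growth, leaving out a baseline measurement of the same quantity gives up precision at no saving.

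**Working it through.** **Inputs from the Protocol.** Entry is at age 70 days or less (6.1), follow-up runs to age 48 months (8.1), attrition is about 10%, and 480 are recruited for 220 per arm (11.2).

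**The plan's own figure.** 2 x 220 = 440, and 440/0.90 = 489 against the stated 480, a gap of 1.9%. This is consistent with approximately 10%. Section 11.2 gives no split by arm. It ties the allowance to a per-protocol comparison, so it does not say how much is lost follow-up.

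**Planned follow-up.** A child entering at 70 days has 48 - 70/30.44 = 45.7 months, at most 4.8% below 48. By design, follow-up is nearly equal.

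**Effect of withdrawal on totals.** If a fraction d withdraws at times spread evenly over follow-up, mean follow-up is 1 - d/2 of the plan.
- 10% in both arms: 0.95/0.95 = 1.00. The ratio is intact and the mean difference shrinks by 5%.
- 5% versus 15%: 0.975/0.925 = 1.054.
- 0% versus 20%: 1.00/0.90 = 1.11.

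**False-positive rates with no true difference.** Simulation with gamma-Poisson counts, 240 per arm, 4,000 runs, two-sided 5%. The simulation error at a true 5% is sqrt(0.05 x 0.95/4000) = 0.34 percentage points. Event means, dispersion (0.5 at mean 10, 2 at mean 1) and withdrawal patterns are assumptions, because the Protocol gives none.

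| Withdrawal by arm | Mean events per child | Ratio of totals | t test | Mann-Whitney | Ratio of events per person-time |
|---|---|---|---|---|---|
| 10% v 10% | 10 | 1.000 | 5.6% | 5.4% | 0.999 |
| 10% v 10% | 1 | 1.002 | 4.5% | 4.9% | 1.003 |
| 5% v 15% | 10 | 1.053 | 10.3% | 13.2% | 0.999 |
| 5% v 15% | 1 | 1.056 | 5.9% | 5.9% | 1.002 |
| 0% v 20% | 10 | 1.110 | 29.2% | 40.5% | 0.999 |
| 0% v 20% | 1 | 1.110 | 10.0% | 10.8% | 0.999 |

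A second set at 3 courses a year for 3.83 years (3 x 3.83 = 11.5 per child), dispersion 0.5, gave 11.0% and 13.7% at 15% versus 5%, and 5.7% and 6.2% at 12% versus 8%. Varying dispersion from 0.25 to 1 at 15% versus 5% gave 8-15% and 10-18%. At about one event per child it gave 6.7% and 7.3%.

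**Power, true ratio 0.80, mean 10.** Without withdrawal the mean difference is -1.985, with power 86.9% (t) and 81.8% (Mann-Whitney). With 10% withdrawal in both arms the difference is -1.877 and power is 84.0% and 76.2%. With 5% withdrawal in the lower-rate arm and 15% in the other, the ratio of totals moves to 0.842 and power falls to 62.1% and 46.2%. Events per person-time still give 0.799.

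**Growth.** Adjusting for a baseline value with correlation r to the outcome multiplies the variance by 1 - r². At r = 0.3 this is 0.91 (9% less). At r = 0.5 it is 0.75 (25% less). The correlation between early infancy and about 48 months is assumed.

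**Extra antibiotic.** A child in Detect and Treat has no antibiotic prescribed by the arm, so under 8.2.2 every day of prophylaxis after a switch is additional. For illustration, if 10% of that arm spent two years on it, the arm mean would rise by 0.10 x 730 = 73 days per child.

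**The case against.** **The bias needs unequal withdrawal.** A reader might infer that the stated tests bias the counts outright. The documents do not support that. Follow-up runs to a common age, 11.2 assumes no difference between arms, and equal withdrawal leaves the error rate near 5%. Stopping treatment does not end follow-up (8.5.2), which limits truncation further. This stands, and the bias is conditional.

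**Missing-data plan.** Section 11.3 describes complete-case analysis with imputation sensitivity analyses. If children with incomplete totals were excluded, 15% versus 5% gives 5.6% and 4.7%, provided withdrawal is unrelated to outcome. But 8.5.3 keeps partial data, so the documents allow either reading, and exclusion discards observed time.

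**Left to the analysis plan.** Count models and covariates often belong there, and 11.3 speaks of continuous data without naming these outcomes. Even so, it states a method, the analysis plan is to elaborate that method, and no other stated rule can cover the totals. Applying it to them is an inference, but a fair one.

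**Other inferences that do not hold.**
- *Choosing the test on the data inflates error.* Selection by a normality check gave 5.0% to 5.2%. The fault is the undefined effect measure.
- *The rule drives early stopping.* Section 8.7 lists hospital days and IV antibiotics as possible grounds, but 11.3 plans no formal interim analysis of secondary outcomes.
- *Aerosolised antibiotics go unrecorded.* Section 9.5.3 has "any additional antibiotics (oral/ IV) prescribed since the last encounter", but the same section also records any medication started or changed, and 8.2.2 records all medication and lists the aerosolised route.
- *The growth time points conflict.* Table 1 has "At 48 months (or as near to study end as possible"), while 8.2.4 has "the analysis will focus on this outcome in the last 8 months of the trial (age 40-48 months"). The second can be read as carrying out the first.
- *Unequal follow-up distorts growth.* An age-standardised score near study end is not a total, and an unadjusted randomised comparison of it is valid.
- *Alternative prophylaxis after intolerance counts as extra.* It can equally be read as a substitute for the allocated drug. The switch from Detect and Treat is the clear case.

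**Conclusion.** The point holds in a limited form. The stated rule for antibiotic and admission totals ignores follow-up time and leaves the effect measure open. Under equal withdrawal the cost is small: differences attenuated by about 5% and, at mean 10, about 3 points of t test power. Under an assumed 15% versus 5%, the ratio of totals is about 1.05, with false-positive rates of about 11% and 14% for frequent events and 6-7% for rare ones. These figures rest on assumed event rates, dispersion and withdrawal timing. Nothing in the documents shows that withdrawal will differ, but an open-label design cannot exclude it.

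The growth point concerns precision only, at 9-25% of variance if the correlation is 0.3 to 0.5. The definition of extra antibiotic needs no statistical assumption: as worded, it admits prophylaxis after a switch. Only its size (73 days in the example) is hypothetical.

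**What to change.** - **Counts.** Prespecify a negative binomial or similar overdispersed count model for courses, antibiotic days, stays and inpatient days, with log follow-up time as offset, and report rate ratios with confidence intervals. This replaces the choice between two tests.
- **Growth.** Analyse weight and height SD scores at 40-48 months by regression adjusted for the baseline SD score.
- **Antibiotics.** Tally prophylactic antibiotic days separately from treatment courses in both arms, and say in 8.2.2 how prophylaxis after a switch or substitution is classed.
- **Tidying only.** Align the route wording in 9.5.3 with 8.2.2, and the growth time point in Table 1 with 8.2.4.

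The cost is revised wording, slightly more analysis work and no new visits. The downside is model dependence. The offset assumes a roughly constant event rate over follow-up and corrects for unequal time, not for withdrawal that is itself related to a child's event rate. The planned sensitivity analyses remain necessary.
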